#### 8.2.1.2 GSP Data Outlier

The GSP assessment is known to be a highly variable measure. As such, two approaches will be applied to reduce the influence of large variations:

- 1) Prior to performing missing data imputations, if Normality of the GSP change from baseline to EOT data is violated by the Shapiro-Wilk test for either the vehicle arm or the sofpironium bromide gel, 15% arm, the GSP data will be rank-transformed at baseline and EOT and the difference in ranks will be used as the dependent variable in the primary efficacy model (Section 8.3.2)
- 2) Outlying GSP values will be removed from the imputation sampling database for missing data imputation purposes, as described below

In order to ensure that the missing data imputation method proposed is robust to outliers for the GSP co-primary endpoint, data from subjects that meet the criterion for being an outlier will be removed from the imputation sampling database as follows. Combining the vehicle and sofpironium bromide gel, 15% arms, the mean and standard deviation will be calculated for the non-missing GSP change from baseline to EOT data, i.e. the GSP primary outcome measure. Data values more than 3 standard deviations away from the mean will be regarded as outliers. However, since the outliers are included in the original mean and standard deviation calculations and would have inflated their values. the outliers will be set aside and the mean and standard deviation will be re-calculated to see if any additional outliers are identified. This process will be repeated until no more outliers are identified. Prior to performing imputation for missing GSP change from baseline data in the ITT population (Section 8.2.1.1) data values contributing to the outlying observations will be removed from the imputation sampling database, i.e. the non-missing vehicle data. With this approach, outlying data will not be propagated during missing data imputation. Once an imputation is complete, all original non-missing data (including outliers) and the imputed, previously missing, data will be used for the GSP ITT analysis.

### 8.2.1.3 Missing Data for all other Efficacy Endpoints

Unless otherwise specified, missing GSP and HDSM-Ax EOT data will be imputed for all ITT efficacy analyses.

#### 8.2.2 Multicenter Studies

Subjects from low enrolling sites will be pooled in order to generate analysis centers. The minimum number of subjects per analysis center is 10. For sites with <10 enrollments, the lowest enrolling site will be combined with the largest enrolling site, and then the second lowest enrolling site and the second largest enrolling site will be combined, and so on. Further combining will be done as necessary until all analysis centers have at least 10 subjects. All analyses that are controlled for site will use this analysis center designation.

Version: 2.0 Page 26 of 74

Should convergence issues occur due to small cell size for the covariate corresponding to analysis center, the following approach will be followed: a) analysis center will first be re-defined, continuing to group the largest and smallest centers together until there are at least 35 subjects per center; b) If convergence issues still occur after step a) has been completed then analysis center will be re-defined again, continuing to group the largest and smallest centers together until there are at least 70 subjects per center; c) if convergence issues still remain after implementing steps a) and b), the term for analysis center will dropped from the MI algorithm/statistical model.

If the convergence issue occurs in the generation of a MI dataset, all outcomes based on that dataset will use the same analysis center definition. All sensitivity analysis datasets will use the same analysis center definition and the models based off of those datasets will use that analysis center definition.

If the convergence issue occurs in modeling of an outcome, all models for that particular outcome will use the same analysis center definition. For example, if the grouping of at least 70 subjects per analysis center is required for the EOT analysis of  $\geq$ 2-point improvement in HDSM-Ax-7, then all models at all time points of the  $\geq$ 2-point improvement in HDSM-Ax-7 will use that analysis center definition. However, this would not impact the choice of analysis center for  $\geq$ 1-point improvement in HDSM-Ax-7, nor the  $\geq$ 2-point improvement in HDSM-Ax-11.

#### 8.2.3 Assessment Time Windows

Allowable windows for each study visit are laid out in the Schedule of Events in Section 18.1. Assessments that occur outside of the allowable window for each study visit will be flagged as protocol deviations, but will be used in all analyses. In general, all data will be associated with the nominal study visit for which it was collected. Repeat assessments and unscheduled visits will be included in study listings, but will not be used in place of nominal timepoint data. It is not expected that there will be multiple measurements that occur within the same assessment time window. Should that occur, the closest measurement will be used in the analysis; an earlier measure will be used in case of a tie.

#### 8.2.4 Multiple Comparisons/Multiplicity

A gated, fixed-sequence testing procedure will be used in this protocol to control the overall familywise false positive error rate for the primary and secondary endpoints analyses. The primary analysis will be regarded as positive and the trial will be successful for the co-primary efficacy endpoints if both null hypotheses are rejected in favor of sofpironium bromide gel, 15% at the 2-sided alpha = 0.05 level of significance (see hypotheses defined in Sections 8.3.1 and 8.3.2).

The three secondary efficacy endpoints are described in Section 8.1.3. If both co-primary analyses yield statistically significant results in favor of the sofpironium bromide gel, 15%, group, the three secondary efficacy endpoints will be tested in a fixed sequence in the order presented in Section 8.1.3. Testing will continue only if all previously tested

Version: 2.0 Page 27 of 74

null hypotheses have been rejected at the 2-sided alpha = 0.05 significance level in favor of sofpironium bromide gel, 15%.

#### 8.2.5 Electronic Clinical Assessment Data

Gravimetric measurements of sweat production (GSP) and patient-reported outcomes HDSM-Ax, PGI-S, PGI-C, and Dermatology Life Quality Index (DLQI) (via electronic clinical outcomes assessment [eCOA] technology) will be recorded during the study at predefined timepoints. In the event that the eCOA data is not able to be captured via a device, the assessments will be recorded manually and the data entered into EDC. It is not expected that a subject will record both an electronic and a manual assessment for an outcome at any given timepoint. However, if duplicate data do exist, then the eCOA value will be used in the analysis.

## 8.3 Analysis Methods

With the exclusion of Section 8.3.7 Exploratory Efficacy Analyses, all other Section 8.3 analyses will be repeated for the mITT population.

The primary efficacy analysis will be performed on the ITT population with missing values imputed. The co-primary efficacy outcomes are:

- The proportion of subjects achieving at least a 2-point improvement in the HDSM-Ax-7 scale score from baseline to EOT in the sofpironium bromide gel, 15% group versus vehicle; and
- The change in GSP from baseline to EOT in the sofpironium bromide gel, 15% group versus vehicle.

Both comparisons will be conducted using two-sided tests at an alpha=0.05 level. Both endpoints will need to demonstrate a statistically significant positive result in favor of sofpironium bromide gel, 15% for the study to be considered successful.

# 8.3.1 Primary Analysis of the HDSM-Ax-7 Co-Primary Endpoint

The primary analysis of the HDSM-Ax-7 co-primary endpoint will use the 2-point responder status at EOT. If a subject is missing any of items 1a, 1b, 2a, 2b, 2c, 2d, or 2e Visit 4 (Day 1) value, Visit 1 (Screening) value will be used as Baseline. If Visit 1 (Screening) value is also missing, subject will be excluded from all HDSM-Ax-7 change from baseline analyses. If a subject is missing Day 43 value, the closest (in time) available non-missing value from Day 41 (±2 days) or Day 42 (±2 days) will be used as the first level of imputation. Should none of the Days 41, 42, and 43 values be available, multiple imputations of missing EOT (i.e. Day 43) item-level scores will be performed on the sofpironium bromide gel, 15% arm values using CBI methodology (Section 8.2.1.1 and Appendix 18.2). Multiple imputations assuming MAR will be performed for missing data for Vehicle subjects. The HDSM-Ax-7 score will be calculated using the imputed item-level values. No other missing value imputation will be performed in this coprimary analysis.

Version: 2.0 Page 28 of 74

The analysis will use a logistic regression model.

The following covariates are planned:

- Treatment (class effect: sofpironium bromide gel, 15% group, vehicle)
- Baseline HDSM-Ax-7 total score
- Analysis center (see Section 8.2.2)

The null hypothesis to be tested for the primary analysis of the HDSM-Ax-7 co-primary endpoint is as below:

H0: The proportion of subjects achieving at least a 2-point improvement in the HDSM-Ax-7 scale score from baseline to EOT is the same in the sofpironium bromide gel, 15%, and vehicle groups, i.e.

$$H_0: P_A = P_P:$$

where  $P_A$  and  $P_P$  represent the true underlying proportion of subjects achieving at least a 2-point improvement in HDSM-Ax-7 for Treatment A (sofpironium bromide gel, 15%) and Treatment P (vehicle), respectively.

The null hypothesis will be tested against the two-sided alternative hypothesis as below:

H1: The proportion of subjects achieving at least a 2-point improvement in the HDSM-Ax-7 scale score from baseline to EOT is not the same in the sofpironium bromide gel, 15%, and vehicle groups, i.e.

$$H_1: P_A \neq P_P:$$

Within the model specified above, a comparison will be made of the proportion of  $\geq$ 2-point HDSM-Ax-7 responders at EOT in the sofpironium bromide gel, 15%, and vehicle groups. The estimand of this co-primary efficacy analysis is the difference in proportions between sofpironium bromide gel, 15%, and vehicle with a  $\geq$ 2-point improvement from baseline to EOT in HDSM-Ax-7 total scores among all ITT subjects, regardless of treatment adherence. The comparison will be conducted using a two-sided test at an alpha = 0.05.

A separate, site poolability analysis will be performed with analysis center-by-treatment interaction terms added to the primary analysis model. The overall p-value for the analysis center-by-treatment interaction terms will be determined by averaging the Chi-squared test statistics across the 20 imputations, then calculating the p-value based on that average. An overall p < 0.10 for the combined interaction terms will be regarded as an indication of potential heterogeneity among the analysis centers. A mixed effects logistic regression model analysis will then be performed with analysis center as a random effect to account for the potential heterogeneity. The overall p-value for the analysis center random effect will be derived from the covariance parameter estimates across the 20 imputations.

Version: 2.0 Page 29 of 74

30 July 2021

#### 8.3.2 **Primary Analysis of the GSP Co-Primary Endpoint**

The primary analysis of the GSP co-primary endpoint will use all available GSP change from baseline scores at EOT. Missing baseline continuous GSP data (i.e. missing data for all Visits of 2, 3, 4) will be imputed using the Screening GSP data. If Screening GSP data is also missing, subject will be excluded from all GSP change from baseline analyses.

For GSP change from baseline to EOT data, univariate checks will be performed prior to performing multiple imputations for missing data. The Shapiro-Wilk test will be applied to assess Normality of the model residuals separately for sofpironium bromide gel, 15% arm, and vehicle arm. Should the assumption of Normality not be violated for both treatment arms, then GSP change from baseline to EOT values will be analyzed as continuous data. The median of continuous GSP data from Visits 2, 3, and 4 will be used as the baseline value for a subject, and the median of continuous GSP data from Visits 10, 11, and 12 will be used as the EOT value. For each subject, the difference between the baseline and EOT GSP values (EOT – baseline) will serve as the outcome value for the GSP ANCOVA analysis.

Should the assumption of Normality be violated for either treatment arm, the GSP change from baseline to EOT values will be rank-transformed for both arms. For the ranktransformation of GSP measurements at a particular timepoint, continuous data for all subjects will be ranked together without regard to treatment assignment, from smallest to highest value. The smallest observation will be assigned the rank of 1, the second smallest the rank of 2, and so on. Average ranks will be used for tied observations. For determination of baseline value for a subject, the continuous GSP data will be ranked separately at each of Visits 2, 3, and 4; the median of the three ranks will be used as baseline value of the subject. Using the measurement data from Visits 10, 11, and 12, the rank-transformed GSP value at EOT will be derived in the same manner. For each subject, the difference between the rank-transformed baseline and EOT GSP values (EOT – baseline) will serve as the outcome value for the rank-based GSP ANCOVA analysis.

Missing EOT GSP data (continuous data), for each of Days 41, 42, and 43 will be imputed before analysis is performed for subjects missing both axillae at all 3 visits. If at least one axillae is non-missing at Day 41, 42, or 43, then the EOT value will be considered non-missing. For continuous data, subjects with results (Section 8.2.1.2) meeting the criterion for "outlier" will be removed from imputation sampling database (i.e., data for vehicle subjects) prior to missing data imputation. From the appropriate imputation sampling database, multiple imputations of missing EOT sofpironium bromide gel, 15% arm GSP values will be performed using a CBI methodology (Section 8.2.1.1 and Appendix 18.3). Multiple imputations assuming MAR will be performed for missing EOT data Vehicle subjects.

The model specified is an ANCOVA model (either non-ranked or ranked).

The following fixed effects are planned:

Treatment (class effect: sofpironium bromide gel, 15% group, vehicle)

Version: 2.0 Page 30 of 74

- Baseline GSP (either non-ranked or ranked)
- Analysis center (see Section 8.2.2)

The null hypothesis to be tested for the primary analysis of the GSP Co-primary endpoint is as below:

H0: The GSP changes (or rank-based changes) from baseline to EOT are the same in the sofpironium bromide gel, 15%, and vehicle groups, i.e.

$$H_0: \mu_A = \mu_P$$
;

where  $\mu_A$  and  $\mu_P$  represent the true mean change (or rank-based change) in GSP scores for Treatment A (sofpironium bromide gel, 15%) and Treatment P (vehicle), respectively.

The null hypothesis will be tested against the two-sided alternative hypothesis as below:

H1: The GSP changes (or rank-based changes) from baseline to EOT are not the same in the sofpironium bromide gel, 15%, and vehicle groups, i.e.

$$H_1: \mu_A \neq \mu_P$$
;

The ANCOVA model used in this analysis will be the same, regardless of whether continuous or rank-based GSP data is used. Within the model specified above, a comparison will be made (using LS mean contrasts) to compare the change (or rank-based change) from baseline to EOT for GSP in the sofpironium bromide gel, 15%, and vehicle groups. The estimand of this co-primary efficacy analysis is the mean treatment difference, sofpironium bromide gel, 15%, versus vehicle, in change from baseline (or rank-based change from baseline) to EOT for GSP among all ITT subjects, regardless of treatment adherence. The comparison will be conducted using a two-sided test at an alpha = 0.05.

For the primary endpoint of either ranked or continuous GSP (pending normality test results), a separate, site poolability analysis will be performed with analysis center-by-treatment interaction terms added to the primary analysis model. The overall p-value for the analysis center-by-treatment interaction terms will be determined by averaging the F test statistics across the 20 imputations, then calculating the p-value based on that average. An overall p < 0.10 for the combined interaction terms will be regarded as an indication of potential heterogeneity among the analysis centers. A mixed effect ANCOVA model analysis will then be performed with analysis center as a random effect to account for the potential heterogeneity. The overall p-value for the analysis center random effect will be derived from the covariance parameter estimates across the 20 imputations.

### 8.3.3 Supportive Analysis of the HDSM-Ax-7 Co-Primary Endpoint

As a supportive analysis of the HDSM-Ax-7 co-primary endpoint, change from baseline to EOT will be analyzed as a continuous measure. The analysis model will be an ANCOVA model with treatment, baseline HDSM-Ax-7 score, and analysis center as

Version: 2.0 Page 31 of 74

covariates. The estimand for this analysis is the difference in mean baseline to EOT changes in HDSMAx-7 total scores between sofpironium bromide gel, 15%, and vehicle arms among all ITT subjects, regardless of treatment adherence.

## 8.3.4 Supportive Analysis of the GSP Co-Primary Endpoint

Two supportive analyses will be performed for the GSP co-primary endpoint:

- (1) If the Shapiro-Wilk test for Normality of the GSP baseline to EOT data is violated, then, using the same methodology as described in Section 8.3.2, an ANCOVA analysis will be performed for the non-rank-transformed, continuous GSP data. The model will use the fixed effects of treatment, baseline GSP, and analysis center. If the Shapiro-Wilk test for Normality of the GSP baseline to EOT data is not violated and the continuous GSP is used for the co-primary endpoint, then the ranked GSP ANCOVA analysis will be performed as a supportive analysis.
- (2) To further address the potential large variations in GSP data, mixed model repeated measures (MMRM) analyses will be performed to estimate the average sofpironium bromide gel, 15% treatment effect over the 6 week course of treatment, i.e. the average sofpironium bromide gel, 15% versus vehicle difference from baseline to Days 8, 15, 22, 29, 36, and EOT, using both rank-based and non-rank-based data. As the MMRM methodology is known to be robust to missing data, missing data will not be imputed for this analysis.

The model specified is a REML-based analysis with an identity link.

The following fixed effects are planned:

- Treatment (class effect: sofpironium bromide gel, 15% group, vehicle)
- Visit (visits will be coded as ordinal, where Visit 5 = 1, Visit 6 = 2, Visit 7 = 3, Visit 8 = 4, Visit 9 = 5, EOT = 6)
- Baseline GSP (ranked or non-ranked, depending on the model)
- Analysis center
- Baseline-by-visit interactions
- Treatment-by-visit interactions

Based on the Study BBI-4000 CL-203 results, significant treatment versus visit interactions are not expected. Nevertheless, should treatment versus visit interactions be significant (i.e. p<0.05), the estimated treatment effect at EOT will be reported. An unstructured correlation matrix will be used to model the variance and covariance of within-subject repeated measures and restricted maximum likelihood estimation. The Kenward-Roger method will be used for the denominator degrees of freedom. In order to arrive at the correct structure for the data, if the model fails to converge using an unstructured covariance matrix, other covariance structures will be tested as follows: heterogeneous Toeplitz (TOEPH), heterogeneous AR(1) (ARH1), heterogeneous compound symmetry (CSH), Toeplitz (TOEP), spatial power with numeric visit number

Version: 2.0 Page 32 of 74

SP(POW)(VISn), autoregressive (1) (AR(1)), and compound symmetry (CS). The model that converges with the lowest Akaike Information Criterion (AIC) will be used. If the treatment-by-visit interactions are not significant overall, they will be removed from the final model; similarly for the baseline-by-visit interactions.

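### In the supportive GSP MMRM, a p<0.05 interaction pretest decides whether a common treatment coefficient or the EOT effect is reported, so the stated six-visit average is not assured when effects vary by visit

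*SAP*

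**What the plan says.** SAP Section 8.3.4, supportive analysis (2), states its purpose as "to estimate the average sofpironium bromide gel, 15% treatment effect over the 6 week course of treatment", which it spells out as "the average sofpironium bromide gel, 15% versus vehicle difference from baseline to Days 8, 15, 22, 29, 36, and EOT". Protocol Section 10.3.2(b) gives the same target and leaves the model details to the SAP.

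The SAP model has treatment, visit, baseline GSP, analysis center, baseline-by-visit and treatment-by-visit, with an unstructured within-subject covariance and a list of fallback structures. It is fitted to ranked and to continuous GSP without imputation. Two rules follow:

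- Interaction significant: "should treatment versus visit interactions be significant (i.e. p<0.05), the estimated treatment effect at EOT will be reported".
- Interaction not significant: "If the treatment-by-visit interactions are not significant overall, they will be removed from the final model; similarly for the baseline-by-visit interactions".

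Both documents say that no (significant) interaction is expected, citing study BBI-4000-CL-203. Under SAP Section 8.1.1, EOT GSP is the median of Visits 10, 11 and 12. Days 8 to 36 are one visit each.

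**The concern.** The target is fixed in advance, but the reported quantity is chosen by a test on the data. The two branches can give different quantities, and neither is written as an equally weighted contrast of the six visit differences. The EOT branch is entered when the effect appears to change over time, which is when the EOT effect and the average differ. The other branch forces one coefficient on all visits, and under an unstructured covariance the fitted covariance sets the visit weights. If the test has low power, a real trend will often go undetected and the term will be dropped.

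At stake is the meaning of a supportive result that was added to draw on the whole treatment period because single GSP readings are so variable.

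**Working it through.** The plan gives no figure to reproduce. The check is what each branch estimates.

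**Inputs from the documents.** Six visits; interaction test at 0.05; unstructured covariance; about 300 evaluable subjects, so 150 per arm; 73 mg and SD about 170 (SAP Section 2.6), used only for scale.

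**Assumptions.** The documents give neither between-visit correlations, nor the variance of EOT relative to a single visit, nor an effect path. I take SD 170 at a single visit, complete data, and two paths from -40 to -73 mg:

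- straight: -40, -46.6, -53.2, -59.8, -66.4, -73; mean -339/6 = -56.5
- concave: -40, -50, -58, -64, -68, -73; mean -353/6 = -58.8

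**Formulas.** With the interaction removed, the treatment coefficient estimates w'd, where d holds the six visit differences and w = S⁻¹1 / (1'S⁻¹1) for visit covariance S. If every element of d is the same, w'd equals that value whatever S is. The standard error is √[(2/150)/(1'S⁻¹1)], against √[(2/150)(1'S1)/36] for the equally weighted mean. Interaction power comes from a non-central chi-square on 5 df.

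**Results with EOT less variable than a single visit** (straight / concave path):

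| Correlation; EOT variance ratio | EOT weight | Target, mg | Gap from average, mg | Interaction power | SE reduced / equal-weight, mg |
|---|---|---|---|---|---|
| Compound symmetry 0.5; 0.7 | 0.39 | -61.0 / -62.7 | 4.5 / 3.8 | 0.32 / 0.31 | 14.3 / 14.6 |
| Compound symmetry 0.6; 0.6 | 0.61 | -65.4 / -66.4 | 8.9 / 7.6 | 0.41 / 0.39 | 14.5 / 15.4 |
| AR(1) 0.7; 0.7 | 0.53 | -59.6 / -60.5 | 3.1 / 1.7 | 0.16 / 0.16 | 13.3 / 14.4 |

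First row, straight path: 0.1216 × (-266) + 0.392 × (-73) = -32.3 - 28.6 = -61.0. In the AR(1) row the Day 36 weight is slightly negative (-0.04). Equal weighting would give EOT 1/6 = 0.17.

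**A milder case.** Take a stable subject effect plus independent normal error, with EOT a median of three. Its error variance is 1 - √3/π = 0.449 of a single reading's, so its weight is (1/0.449)/(5 + 1/0.449) = 2.23/7.23 = 0.31 at any correlation.

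**Equal visit variances.** Compound symmetry gives every visit 1/6 and a gap of zero. AR(1) 0.7 gives the first and last visits 0.31 each, with a gap of zero on the straight path and about 1 mg on the concave one. Interaction power falls to 0.13 under AR(1) 0.6.

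**Near-constant effect** (-65 rising evenly to -73): gaps of 1.1, 2.2 and 0.8 mg in the three table scenarios.

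**The two branches, simulated** (150 per arm, 4000 trials, SD 170 at every visit):

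- Constant -73 mg: the test is significant in 4.9% (compound symmetry 0.5) and 5.2% (AR(1) 0.6) of trials. The rest report a mean of -73.1 and -73.0 mg.
- Effect growing from -45 to -95 mg, average -73: the EOT branch is taken in 62% and 26% of trials and reports a mean of -99 and -107 mg, beyond the true EOT effect of -95 because it is reported only after a significant test. The remaining trials report -73.0 and -72.0 mg.

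**The case against.** A reader might infer that the six-week average is never reported, or that the analysis mostly repeats the EOT result. The documents support neither. With the interaction gone, the treatment term is one difference common to all six visits, and under a constant effect that is the six-week average. Protocol Section 1 says the response in earlier studies appeared by Day 8 and stayed consistent, and both documents expect no interaction, so this is the expected path. In the three table scenarios the visits before EOT still carry 39% to 61% of the weight. Nor does the SAP say that only the EOT effect will be shown in the significant branch; it just does not promise the average there.

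The assumed growth runs against the documents' own expectation, every covariance above is assumed, and the gaps are smaller than one standard error. Reporting a visit-specific effect when effects differ by visit is a recognised prespecified choice. The time course will also be visible elsewhere: SAP Section 8.3.7 and Tables 14.2.3.39 to 14.2.3.44 cover ranked, absolute and percent GSP change by visit, and the EOT effect is the co-primary result.

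All of this stands, and it limits the size of the point. It does not remove the data-dependent choice of what is reported, or supply an equally weighted six-visit estimate when effects vary.

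**Conclusion.** The point holds as a minor one. The SAP names one target and then lets a p<0.05 test choose between a common coefficient and the EOT effect. When the effect is constant, the coefficient is the target. When it varies, the coefficient is a precision-weighted mean, and in the significant branch the SAP makes no commitment to report the average.

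The size rests on assumed inputs. For growth from -40 to -73 mg the gap is about 2 to 9 mg if EOT is less variable than a single visit, and near zero if visit variances are equal, against a standard error of 13 to 15 mg. Interaction power is then about 0.13 to 0.41, so such a trend would usually be missed. For a near-constant effect the gap is at most about 2 mg.

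The MMRM is supportive and outside the fixed sequence in SAP Section 8.2.4, so neither trial success nor the familywise error rate is affected.

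**What to change.** In SAP Section 8.3.4, delete the rule that removes non-significant interactions and the rule that switches to the EOT effect. Keep treatment-by-visit and baseline-by-visit in the model whatever their p-values. Always report two estimates, each with a confidence interval, for ranked and for continuous GSP:

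1. the equally weighted mean of the six visit-specific LS-mean differences;
2. the LS-mean difference at EOT.

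The interaction p-value can still be shown as description.

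The cost is SAP wording, an added contrast statement and a few degrees of freedom. The standard error of the average rises by about 2% to 8% in the table scenarios (14.6/14.3, 15.4/14.5 and 14.4/13.3). No extra visits or subjects are needed.
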